2. LIST OF ABBREVIATIONS

Abbreviation	Definition
ADR	adverse drug reaction
AE	adverse event
ALT	alanine transaminase
ANC	absolute neutrophil count
AST	aspartate aminotransferase
AUC	area under the concentration-time curve
BCRP	breast cancer resistance protein
β-hCG	beta human chorionic gonadotropin
BOR	best overall response
CBC	complete blood count
CBR	clinical benefit rate
CDK4/6	cyclin-dependent kinase 4/6
cfDNA	cell-free DNA
CFR	Code of Federal Regulations
CI	confidence interval
CL/F	apparent oral clearance
CLIA	Clinical Laboratory Improvement Amendments
C_{max}	maximum concentration
CNS	central nervous system
CR	complete response
CT	computed tomography
CTCAE	Common Terminology Criteria for Adverse Events
CV	coefficient of variation
CYP	cytochrome P450
DDI	drug-drug interaction
DLT	dose-limiting toxicity
EC ₅₀	50% effective concentration
ECG	electrocardiogram
ECOG	Eastern Cooperative Oncology Group
eCRF	electronic case report form
EGFR	epidermal growth factor receptor
ER	estrogen receptor
FDA	Food and Drug Administration

Abbreviation	Definition
FDG-PET	positron emission tomography with 2-deoxy-2-[fluorine-18]fluoro-D-glucose
FGFR	fibroblast growth factor receptor
FIH	first-in-human
G1	gap 1 phase of the cell cycle
GCP	Good Clinical Practice
G-CSF	granulocyte colony-stimulating factor
GEMM	genetically engineered mouse model
HDPE	high-density polyethylene
HED	human equivalent dose
HER2	human epidermal growth factor receptor 2
hERG	human ether-à-go-go related gene
HR	hormone receptor
HRCT	high-resolution computed tomography
IB	Investigator's Brochure
IC_{50}	50% inhibitory concentration
ICH	International Council for Harmonisation
IDMC	independent data monitoring committee
IEC	independent ethics committee
IGF1R	insulin-like growth factor 1 receptor
ILD	interstitial lung disease
IMP	investigational medicinal product
IRB	institutional review board
IWRS	interactive web-response system
LD	longest diameter
LVEF	left ventricular ejection fraction
MATE1 or 2-K	multidrug and toxin extrusion 1 or 2-K
MedDRA	Medical Dictionary for Regulatory Activities
MRI	magnetic resonance imaging
MTD	maximum tolerated dose
MUGA	multigated acquisition
NCI	National Cancer Institute
NE	not evaluable
NSCLC	non-small cell lung cancer
NTL	nontarget lesion
NYHA	New York Heart Association
OCT1 or 2	organic cation transporter 1 or 2

Abbreviation	Definition
ORR	overall response rate
OS	overall survival
PD	progressive disease
PET	positron emission tomography
PFS	progression-free survival
P-gp	P-glycoprotein
PK	pharmacokinetic(s)
PP	per protocol
PR	partial response
PTV	Post-Treatment visit
QTc	QT interval corrected for heart rate
Rb	retinoblastoma protein
RBC	red blood cell
RECIST	Response Evaluation Criteria in Solid Tumors
RP2D	recommended Phase 2 dose
S	synthesis phase of cell cycle in which DNA is replicated
SAE	serious adverse event
SAP	statistical analysis plan
SD	stable disease
SMC	safety monitoring committee
SOC	system organ class
SOP	standard operating procedure
SUSAR	suspected unexpected serious adverse reaction
$t_{1/2}$	terminal half-life
TEAE	treatment-emergent adverse event
TKI	tyrosine kinase inhibitor
T_{max}	time to reach C _{max}
ULN	upper limit of normal
US	United States
V_z/F	apparent volume of distribution during the terminal phase
WHO	World Health Organization

3. SYNOPSIS

Title	Phase 1b/2 Safety, Pharmacokinetic, and Efficacy Study of G1T38 in
	Combination with Osimertinib in Patients with EGFR
	Mutation-Positive Metastatic Non-Small Cell Lung Cancer (NSCLC)
Study Rationale	Non-small cell lung cancers (NSCLCs) represent the vast majority of lung cancers around the world, and epidermal growth factor receptor (EGFR) mutations occur in approximately 15% of NSCLCs in the United States and up to 62% of NSCLCs in Asia. Osimertinib (Tagrisso®) has been established as the second-line standard of care in EGFR-positive NSCLC with a T790M mutation after failure of a first-line EGFR tyrosine kinase inhibitor (TKI), and has also recently demonstrated benefit in first-line EGFR-positive NSCLC regardless of T790M status. Historical median progression-free survival (PFS) with second-line osimertinib monotherapy is approximately 10 months, and the overall response rate (ORR) is approximately 70%. Nearly all patients eventually develop resistance to osimertinib and experience disease progression.
	The putative resistance mechanisms to osimertinib include activating mutations in PIK3CA, MEK1, and KRAS; amplifications in MET, HER2, and FGFR1; activation of the IGF1R pathway; and EGFR C797S mutation. Many of these are upstream of cyclin-dependent kinase 4/6 (CDK4/6), suggesting that combining G1T38 with osimertinib has the potential to block these resistance pathways, delay the time to resistance, prolong PFS, and thus delay the need for cytotoxic chemotherapy.
	In a well-established, erlotinib-resistant, T790M-positive NSCLC murine model, adding G1T38 to erlotinib treatment resulted in a 77% delay in tumor growth compared with erlotinib alone; whereas, erlotinib alone showed no statistically significant change compared with vehicle control. Furthermore, the addition of G1T38 to afatinib treatment nearly doubled the time to resistance when compared with treatment with afatinib only. Finally, in murine tumors that became resistant to afatinib, the addition of G1T38 caused stable disease (SD). These results suggest that the addition of G1T38 to an EGFR inhibitor could potentially extend PFS in patients with NSCLC.
Clinical Phase	1b/2
Indication	Treatment of EGFR T790M mutation-positive metastatic (Stage IV) NSCLC after first-line EGFR TKI failure

Objectives

	Part 1 (Phase 1b)	Part 2 (Phase 2)
Primary Objectives		
Evaluate DLTs associated with G1T38 administered with osimertinib	X	
Determine the recommended Phase 2 dose of G1T38 administered with osimertinib	X	
Evaluate the safety and tolerability of G1T38 administered with osimertinib	X	X
Assess PFS using BICR (RECIST v1.1)		X
Secondary Objectives		
Assess the effect of osimertinib on PK parameters of G1T38	X	
Assess PFS using investigator assessments (RECIST v1.1)	X	X
Assess response rate and CBR based on RECIST v1.1 (BICR and investigator assessed)	X	X
Assess OS	X	X
Assess 1-year PFS (BICR and investigator assessed)	X	X

CBR = clinical benefit rate; cfDNA = cell-free deoxyribonucleic acid;
DLT = dose-limiting toxicity; NSCLC = non-small cell lung cancer; OS = overall survival; PFS = progression-free survival; PK = pharmacokinetic; RECIST = Response Evaluation Criteria in Solid Tumors; BICR = blinded independent central review

Study Design

This is a Phase 1b/2, multicenter, open-label study of the safety, tolerability, pharmacokinetics (PK), and efficacy of G1T38 in combination with osimertinib for patients with EGFR mutation-positive metastatic NSCLC. This open-label study consists of 2 parts: Part 1 will evaluate the effect of osimertinib on the PK parameters of G1T38 and the safety and tolerability (including dose-limiting toxicities [DLTs]) of escalating doses of G1T38 in combination with osimertinib to determine the recommended Phase 2 dose (RP2D); and Part 2 will be a randomized portion to further evaluate the safety, tolerability, and efficacy of the RP2D. Both parts of the study include 3 study phases: Screening Phase, Treatment Phase, and Survival Follow-up Phase. The Treatment Phase begins on the day of the first dose of study drug and completes at the Post-Treatment visit.

Part 1

Part 1 Pharmacokinetic Interaction and Dose-Escalation Cohorts

Cohort 1: Six patients will be enrolled in the first cohort in Part 1 to assess the potential effect of osimertinib on the PK parameters of G1T38. G1T38 is a substrate of the breast cancer resistance protein (BCRP) transporter protein and osimertinib has been shown to increase the area under the concentration-time curve (AUC) and maximum concentration (C_{max}) of concurrently administered rosuvastatin, a BCRP substrate, by 35% and 72%, respectively. Patients will receive a single oral dose of G1T38 200 mg on Cycle 1 Day -16 and blood samples for G1T38 PK evaluation will be collected over the subsequent 48-hour period. Patients will then receive oral osimertinib 80 mg once daily without G1T38 on Cycle 1 Days -14 to -3, and then both G1T38 and osimertinib on Cycle 1 Day -2, after which blood samples for G1T38 PK evaluation will be collected over the subsequent 48-hour period. Osimertinib once-daily dosing will continue on Cycle 1 Day -1 and through the end of the Treatment Phase. On Cycle 1 Day 1, patients will begin G1T38 once-daily dosing, which will continue through the end of the Treatment Phase (note: there is no Day 0 in the study). DLTs will be evaluated from Cycle 1 Day -16 through Cycle 1 Day 28 (the DLT period). A safety monitoring committee (SMC) will evaluate all safety and available PK data through the DLT period for Cohort 1 prior to the enrollment of additional cohorts.

Cohorts 2 and beyond: Following completion of Cohort 1, additional sequential dose-escalation cohorts may be enrolled using a standard 3 + 3 design and will follow the same schedule as described for the first cohort. All dose escalation/de-escalation recommendations made by the SMC will be based on review of safety and available PK data from the DLT period of the current cohort, as well as the cumulative safety data from all patients enrolled.

Definition of Dose-Limiting Toxicities

Dose-limiting toxicities are drug-related adverse events (AEs) defined as follows:

- Grade 4 neutropenia
- \geq Grade 3 neutropenic infection/febrile neutropenia
- Grade 4 thrombocytopenia

Clinical Study Protocol G1138	-03 G1138
	 ≥ Grade 3 thrombocytopenia with bleeding ≥ Grade 3 nonhematologic toxicity (additional criterion for nausea, vomiting, diarrhea, or fatigue: lasting > 5 days with maximal medical management) Liver function test abnormalities meeting Hy's Law criteria (aspartate aminotransferase [AST] or alanine aminotransferase [ALT] ≥ 3 × upper limit of normal [ULN] and total bilirubin ≥ 2 × ULN). All study drugs must be permanently discontinued in any patient meeting Hy's Law criteria.
	Part 2
	In Part 2, eligible patients will be enrolled into a randomized portion of the study. Patients will be randomized (1:1) to receive osimertinib or G1T38 (at the RP2D) + osimertinib, with stratification by presence of central nervous system (CNS) metastases (yes versus no) and ethnicity (Asian versus non-Asian). Following screening, patients will begin osimertinib or G1T38 + osimertinib once-daily oral dosing on Cycle 1 Day 1.
	Patients who are initially randomized to receive osimertinib alone may crossover to the G1T38 + osimertinib group at the time of disease progression as determined by blinded independent central review (BICR).
	An independent data monitoring committee (IDMC) shall review all cumulative safety and efficacy data, as well as all available PK data, approximately every 4 months during the Treatment Phase.
Treatment Duration	Study drug administration will continue for each patient until disease progression per RECIST, Version 1.1, unacceptable toxicity, withdrawal of consent, or discontinuation by investigator, whichever occurs first. Patients in Part 2 who are initially randomized to receive osimertinib alone may crossover to the osimertinib + G1T38 arm at the time of disease progression.
Study Duration	Part 1: The duration of Part 1 will be approximately 9 months.
	Part 2: The ORR is expected to read out approximately 1 year after Part 2 enrollment begins. PFS is expected to read out approximately 2.5 years after Part 2 enrollment begins.
	The Survival Follow-up Phase will continue until at least 50% of the patients in Part 2 have died.
Approximate Number of Patients	Overall, up to 144 patients will be enrolled in the study. In Part 1, up to 36 patients may be enrolled. In Part 2, 108 patients will be enrolled.
Number of Study Centers	Approximately 50 centers globally may participate.
Diagnosis and Key Criteria for Inclusion	For a patient to be eligible for participation in this study, all of the following criteria must apply. A full list of inclusion criteria are provided in Section 7.1.1.
	 Women or men, 18 years or older Histologic or cytologic confirmed diagnosis of NSCLC Stage IV NSCLC

• Stage IV NSCLC

- Documented EGFR mutation (at any time since the initial diagnosis of NSCLC) known to be associated with EGFR TKI sensitivity (including G719X, exon 19 deletion, L858R, L861Q)
 - Part 2 Only: Tumor T790M mutation-positive status based on an appropriate test (tumor biopsy or cell-free DNA [cfDNA]) taken after documented disease progression on first-line treatment with a first or second generation EGFR TKI
- Eastern Cooperative Oncology Group (ECOG) performance status of 0 or 1, with no deterioration over the previous 2 weeks and a minimum life expectancy of 12 weeks
- Evaluable (Part 1 only) or measurable disease
- Left ventricular ejection fraction (LVEF) ≥ institution's lower limit of the reference range
- Adequate bone marrow reserve and organ function as demonstrated by the following laboratory values:
 - \circ Hemoglobin ≥ 90 g/L
 - \circ ANC $\geq 1.5 \times 10^9/L$
 - \circ Platelet count $> 100 \times 10^9/L$
 - o Calculated creatinine clearance ≥ 50 mL/minute
 - o Total bilirubin $\leq 1.5 \times ULN$; $< 3 \times ULN$ if the patient has documented Gilbert's disease or liver metastases
 - o ALT $< 2.5 \times$ ULN if no demonstrable liver metastases or $< 5 \times$ ULN in the presence of liver metastases
 - o AST \leq 2.5 \times ULN if no demonstrable liver metastases or \leq 5 \times ULN in the presence of liver metastases

Additional criteria that apply to Part 2 only:

 Measurable disease as defined in RECIST, Version 1.1, as determined by the investigator

Key Criteria for Exclusion

A patient will not be eligible for participation in this study if any of the following criteria apply. A full list of exclusion criteria are provided in Section 7.1.2.

- o Treatment with any of the following:
- EGFR TKIs (erlotinib, gefitinib, afatinib, osimertinib) within
 9 days of the first dose of study drug; other approved EGFR
 TKIs within 5 half-lives of the first dose of study drug
- o Investigational agents within 28 days, or 5 half-lives, whichever is longer, of the first dose of study drug; antibody based therapy within 6 weeks of the first dose of study drug
- o *Part 1 only*: More than 2 prior lines of cytotoxic chemotherapy for advanced NSCLC
- o *Part 2 only*: Any prior cytotoxic chemotherapy for advanced NSCLC
 - Part 2 only: Previous treatment with osimertinib or other T790M active EGFR TKI
- Blood transfusions or hematopoietic growth factor therapy within 14 days of first screening visit
- o Prior radiotherapy treatment to > 25% of the bone marrow or radiotherapy with a wide field of radiation within 28 days of the

first dose of study drug

- Patients receiving medications, herbal supplements, or foods known to be potent inhibitors of cytochrome P450 (CYP)3A4 or orally administered sensitive substrates of CYP3A4 within 14 days prior to first dose of study drug (see Sections 8.5.1 and 8.5.2)
- Patients receiving medications, herbal supplements, or foods known to be potent inducers of CYP3A4 within 21 days prior to first dose of study drug (see Section 8.5.2)
- Patients receiving medications, herbal supplements, or foods known to be potent inhibitors of BCRP within 14 days prior to first dose of study drug (see Section 8.5.2)
- Part 1 only: Patients receiving medications that raise gastric pH within 7 days prior to first dose of study drug (see Section 8.5.5).
- Any unresolved toxicities from prior surgeries or therapy
 Grade 1 (Common Terminology Criteria for Adverse Events [CTCAE] Version 4.03) at the time of starting study drug with the exception of alopecia (any grade) and platinum therapyrelated peripheral neuropathy (> Grade 2)
- Known active uncontrolled or symptomatic central nervous system (CNS) metastases, carcinomatous meningitis, or leptomeningeal disease as indicated by clinical symptoms, cerebral edema, and/or progressive growth. Patients with a history of CNS metastases or cord compression are eligible if they are currently asymptomatic and clinically stable off anticonvulsants and steroids for at least 28 days prior to first dose of G1T38.
- Any evidence of severe or uncontrolled systemic diseases, including uncontrolled hypertension and active bleeding diatheses, which in the investigator's opinion makes it undesirable for the patient to participate in the study or which would jeopardize compliance with the protocol
- Known chronic, active infection
- Cardiac criteria as outlined in Section 7.1.2
- Past medical history of interstitial lung disease, drug-induced interstitial lung disease (ILD), radiation pneumonitis which required steroid treatment, or any evidence of clinically active interstitial lung disease
- o Prior hematopoietic stem cell or bone marrow transplantation

Other Medicinal Products Osimertinib 80 mg orally once daily, with or without food. G1T38 will be administered orally once daily. The starting dose for Part 1 will be a G1T38 dose of 200 mg once daily and subsequent dose levels will be determined by the SMC. All patients in Part 2, will receive the RP2D selected by the SMC. All doses of G1T38 shall be administered with food.

Efficient Evoluation	Efficiency will be assessed by evaluation of tumor response has -1
Efficacy Evaluation	Efficacy will be assessed by evaluation of tumor response based on RECIST, Version 1.1, including objective response rate (ORR), clinical benefit rate (CBR), PFS, and overall survival (OS). Parts 1 and 2 will utilize investigator assessments and Part 2 will also utilize assessments from BICR.
Safety Evaluation	Safety will be assessed by evaluation of AEs, physical examinations, vital signs measurements, clinical laboratory data, echocardiograms/multigated acquisition (MUGA) scans, ophthalmic examinations, and electrocardiograms (ECGs).
Pharmacokinetics Evaluation	In Part 1, serial blood samples will be collected at specified time points from all patients for the measurement of plasma concentrations of G1T38 will be derived from G1T38 plasma concentration-time data. Osimertinib trough concentrations will also be evaluated to confirm compliance.
	In Part 2, a limited number of blood samples shall be collected for population PK analysis of G1T38
Cell-Free DNA Evaluation	Changes in mutational status at selected time points will be assessed and correlated with clinical outcomes.
Statistical Analysis	Data will be summarized separately by study part (Part 1 and Part 2). Data from Part 1 will be summarized descriptively by dose level, if applicable, and overall. Selected safety summaries will include combined data from both Parts 1 and 2 of the study. The descriptive summary for the categorical variables will include counts and percentages. The ORRs and their corresponding 95% exact
	confidence intervals (CIs) will be calculated by Clopper-Pearson method.
	The descriptive summary for the continuous variables will include mean, median, standard deviation (StD), and minimum and maximum. The descriptive summaries of time-to-event data will include median, 25% and 75% percentiles, and standard error. The Kaplan-Meier method will also be used to summarize the time-to-event data. All CIs will be 95%, unless stated otherwise. All data will be listed for all patients.
	For Part 2 of the study, patients will be randomized (1:1) to receive osimertinib or G1T38 + osimertinib. The randomization will be stratified based on presence of CNS metastases (yes versus no) and ethnicity (Asian versus non-Asian).
	PFS assessed by BICR according to RECIST v1.1 is the primary endpoint for Part 2 of the study. The 1-sided stratified log-rank test will be used to compare the 2 treatment groups. A Cox regression analysis with a fixed effect for treatment arm and stratification factors will be used to estimate the hazard ratio (HR) and its 80% CI. OS will be analyzed in a similar way.
	Overall tumor response endpoints such as ORR and CBR are secondary endpoints for Part 2 of the study. A 1-sided stratified Cochran-Mantel-Haenszel (CMH) test will be used to compare the

2 treatment groups. The odds ratio and its associated 80% CI will be presented.

In addition, potential influences of baseline patient characteristics such as age, ECOG performance status, and selected biomarkers on the endpoints may be evaluated to compare the 2 treatment groups.

For Part 2 of the study, because crossover to G1T38 + osimertinib is allowed for patients following progression on osimertinib alone, the treatment effect on OS may be confounded and may not be estimated properly by the above defined methods. Therefore, an exploratory analysis will be performed using the rank-preserving structural failure time (RPSFT) method and Cox model with inverse probability of censoring weighting (IPCW) to correct for confounding introduced by the crossover.

Safety Analysis

The safety analysis will include all treated patients. Descriptive statistics of safety will be presented. All treatment-emergent AEs, drug-related AEs, serious adverse events (SAEs), and drug-related SAEs will be tabulated using worst grade per National Cancer Institute (NCI) CTCAE, Version 4.03 criteria by system organ class and preferred term. On-study laboratory parameters including hematology, chemistry, and liver function tests will also be summarized using worst grade per NCI CTCAE, Version 4.03 criteria.

Rationale for Number of Patients

It is estimated that up to 36 patients will be enrolled in the dose-escalation part of the study (Part 1). The actual number of patients will depend on the number of dose levels/cohorts that are tested.

For the randomized part of the study (Part 2), it is assumed that the overall 1-sided type I error rate is 0.1 and the type II error rate used to compute sample size is 0.20 (corresponding to 80% power). Patients will be randomized using a 1:1 treatment allocation ratio between the 2 treatment groups (osimertinib versus G1T38 + osimertinib).

Assuming a 10.1 month median PFS for the osimertinib group based on historical data, and an HR of 0.6, the required number of PFS events is 70. Assuming an accrual period of 12 months and an additional follow-up period of 18 months after the last patient is enrolled, the calculated total sample size is 98 patients. Allowing for a dropout/lost-to-follow-up rate of approximately 10%, gives an adjusted total sample size of 108 patients for Part 2.

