8.5. Prior and Concomitant Medications and Procedures

All concomitant medications including prescription medications, over-the-counter preparations, herbal remedies, traditional remedies, growth factors, blood products, and parenteral nutrition taken during the 14 days prior to signing the ICF, during the study treatment, and through the Post-Treatment visit shall be documented in the eCRF.

Administration of concomitant, nonprotocol anticancer therapies prior to disease progression is not permitted during the treatment phase of this study. Concomitant radiotherapy and surgeries may be permitted as described in Section 8.8.

Administration of other concomitant investigational agents for any indication is not permitted during the treatment phase of this study.

Medications will be coded by the sponsor or designee using the most recent World Health Organization (WHO) Drug Dictionary version.

If medically feasible, patients taking regular medication(s), with the exception of prohibited medications (see below), should be maintained on those medications throughout the study period.

Refer to Appendix 4 for additional details regarding concomitant medications.

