9.3. Post-Treatment Visit/Early Termination

Patients will return to the study center for a Post-Treatment visit 30 days from the last dose (+ 10 days). The procedures and assessments to be performed at this visit are outlined in Table 9-1 (Part 1) and Table 9-2 (Part 2).

After completing the Post-Treatment visit, patients will enter the long-term Survival Follow-up Phase.

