2.2. Study Design

Study 38-03 is an open-label study evaluating the effect of osimertinib on the PK parameters of G1T38 and the safety and tolerability of escalating doses of G1T38 in combination with osimertinib to determine the RP2D. The study includes 3 phases: Screening Phase, Treatment Phase, and Survival Follow-up Phase. The Treatment Phase begins on the day of the first dose of study drug and completes at the Post-Treatment Visit.

Six patients will be enrolled in the first cohort to assess the potential effect of osimertinib on the PK parameters of G1T38. Projected dose levels are presented in Table 6-1 of the Protocol. Patients will receive a single oral dose of G1T38 200 mg on Cycle 1 Day -16 and blood samples for G1T38 PK evaluation will be collected over the subsequent 48-hour period. Patients will then receive oral osimertinib 80 mg once daily without G1T38 on Cycle 1 Days -14 to -3, and then both G1T38 and osimertinib on Cycle 1 Day -2, after which blood samples for G1T38 PK evaluation will be collected over the subsequent 48-hour period. Osimertinib once-daily dosing will continue on Cycle 1 Day -1 and through the end of the Treatment Phase. On Cycle 1 Day 1, patients will begin G1T38 once-daily dosing, which will continue through the end of the Treatment Phase (note: there is no Day 0 in the study). DLTs will be evaluated from Cycle 1 Day -16 through Cycle 1 Day 28 (the DLT period). A safety monitoring committee (SMC) will evaluate all safety and available PK data through the DLT period for Cohort 1 prior to the enrollment of additional cohorts.

Thereafter, additional sequential dose-escalation cohorts may be enrolled using a standard 3 + 3 design and will follow the same schedule as described for the first cohort.

All dose escalation/de-escalation recommendations made by the SMC will be based on review of safety and available PK from the DLT period of the current cohort, as well as the cumulative safety data from all patients enrolled. Further details with respect to decision making will be described in the SMC Charter.

Patients will be observed for a DLT during the first cycle of treatment (Cycle 1 Day -16 through Cycle 1 Day 28). Please refer to protocol sections 6.1.1.1. for more information regarding the dose escalation plan as it relates to DLT findings.

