4.2.7. Treatment Exposure and Compliance

Prescribed duration of treatment (days) is defined as the total number of days that the patient will have been prescribed study medication, that is, including days on treatment before Cycle 1 Day 1 and days on treatment from Cycle 1 Day 1 to treatment end day. Prescribed duration of G1T38 (months) is calculated as (last dose date on the dosing log – first date of continuous daily dosing (C1D1) + x + 1)/30.4375, where x is the number of days patient received G1T38 before C1D1. For example, for a patient who took one dose of G1T38 each on C1D-16 and C1D-2 respectively and took last dose on or after the first date of continuous, daily dosing of G1T38 (C1D1), Days on Treatment = Date of last dose – C1D1 date + 3; for patients who did not start continuous daily dosing, total number of days on dosing of G1T38 before C1D1 will be used as prescribed duration. Prescribed duration of Osimertinib (months) is calculated as (last dose date on the dosing log - the first date of daily osimertinib (only) dosing (i.e., C1D-14) + 1)/30.4375.

The exposure to G1T38 (months) is calculated by (prescribed G1T38 duration - days of interruption as captured in dosing log)/30.4375. Days of interruption is defined as (start date of next record – end date of current record – 1).

For subjects with last dose date is missing from dosing log, if end of treatment date is not missing, date of end of treatment will be used as last dose date. Otherwise, the later date between the last visit date during the treatment phase and last contact date will be used, but the date must be prior to the start of survival follow-up.

Compliance of G1T38 is expressed as a percentage of days G1T38 was actually taken during the treatment phase and will be calculated as exposure to G1T38 divided by prescribed G1T38 duration multiplied by 100.

Dose reduction will be flagged when a total daily dose recorded in G1T38 dosing log is less than the previous entry. Patient with dose interval change but total daily dose unchanged (e.g. 300 mg QD vs 150 mg BID) will not be considered as dose reduction.

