Safety assessments (other than AEs) during treatment period is defined as assessment that is evaluated between the date of first dose of study drug and the date of last dose of study drug + 29 days. Assessments occur on or after last dose of study drug + 30 days will be counted as assessments during post-treatment period. If start date of survival follow up is available, assessments during post-treatment period should occur prior to the start of survival. If the last dose date of study drug is missing, any assessment/event occurring after the start of study drug will be considered as during treatment period.

All data will be listed for all enrolled patients.

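### SAP 4.2.7's fallback for a missing last-dose date can select the Post-Treatment visit, adding 30 to 40 off-drug days to G1T38 exposure in the rare patient it reaches

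*Protocol*

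**What the plan says.** **The phase.** The protocol synopsis says: "The Treatment Phase begins on the day of the first dose of study drug and completes at the Post-Treatment visit". Protocol 6.1 has the same sentence, and SAP 2.2 carries it over: "The Treatment Phase begins on the day of the first dose of study drug and completes at the Post-Treatment Visit".

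**The visit that closes it.** Protocol 9.3 fixes the timing: "Patients will return to the study center for a Post-Treatment visit 30 days from the last dose (+ 10 days"). It continues: "After completing the Post-Treatment visit, patients will enter the long-term Survival" Follow-up Phase. The Post-Treatment visit is therefore inside the Treatment Phase and before survival follow-up. The visit-window text in SAP 5.1.3 places it there too.

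**Dosing.** The synopsis says that from Cycle 1 Day 1 "patients will begin G1T38 once-daily dosing, which will continue through the end of the Treatment Phase". Protocol 6.1.1 and SAP 2.2 say the same.

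**The fallback.** SAP 4.2.7 handles a last-dose date missing from the dosing log in two steps. It first takes the end-of-treatment date. If that is missing as well, "the later date between the last visit date during the treatment phase and last contact date will be used", provided the date falls before survival follow-up starts.

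**A second rule.** For windowing safety assessments, SAP 5.1.1 says: "If the last dose date of study drug is missing, any assessment/event occurring after the start of study drug will be considered as during treatment".

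**The concern.** The second step of the fallback looks for the last visit in the treatment phase, apparently as a proxy for the last day on drug. By the SAP's own definition, the final visit of that phase takes place at least 30 days after dosing stopped. The rule also takes the later of two dates, so it cannot return anything earlier than the Post-Treatment visit for a patient who attended it. The survival follow-up limit does not help, because follow-up begins only after that visit.

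The limit may also be hard to apply. SAP section 7 says overall-survival data have not been required since 29 January 2020, and SAP 5.1.1 treats the start date of survival follow-up as something that may not be available.

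At stake are the summaries of G1T38 duration, exposure and compliance. These are reported by dose level, in cohorts that may hold only three patients, in a study part with safety and tolerability as a primary objective.

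**Working it through.** **Inputs**
- Post-Treatment visit: last dose + 30 to + 40 days (protocol 9.3).
- Prescribed G1T38 duration in days: last dose − C1D1 + x + 1, where x is the number of G1T38 dosing days before C1D1; divide by 30.4375 for months (SAP 4.2.7).
- Exposure: prescribed duration minus days of interruption. Compliance: exposure ÷ prescribed duration × 100 (SAP 4.2.7).

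**The plan's own figure.** With one dose each on C1D-16 and C1D-2, x = 2. Duration is last dose − C1D1 + 2 + 1 = last dose − C1D1 + 3, which matches the SAP's worked example.

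**Error per affected patient.** Duration moves one for one with the last-dose date:
- 30 / 30.4375 = 0.99 months
- 40 / 30.4375 = 1.31 months

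**Illustration.** Suppose the true last dose is on study day 169.

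| Date used as last dose | Days | Months | SAP 5.2.7 category |
|---|---|---|---|
| Day 169 (true) | 169 − 1 + 3 = 171 | 5.62 | 3 to <6 |
| Day 199 (visit at + 30) | 201 | 6.60 | 6 to <9 |
| Day 209 (visit at + 40) | 211 | 6.93 | 6 to <9 |

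**Compliance.** The added days enter both numerator and denominator, so compliance changes only if there was an interruption. Assume 21 days of interruption:
- True duration 84 days: 63/84 = 75.0% becomes 93/114 = 81.6% to 103/124 = 83.1%. This crosses the 80% category boundary in SAP 5.2.8.
- True duration 168 days: 147/168 = 87.5% becomes 177/198 = 89.4% to 187/208 = 89.9%.

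**Effect of one affected patient on mean exposure**
- Dose level of 3: 0.99/3 to 1.31/3 = 0.33 to 0.44 months
- Dose level of 6: 0.16 to 0.22 months
- All 36 patients: 0.03 to 0.04 months

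**Why 40 days is not a ceiling.** The rule may pick a contact date after the visit. Protocol 8.3.3.2 also lets a patient continue G1T38 after osimertinib is stopped for toxicity, so the last-dose dates of the two drugs can differ. The drug stopped first could then be overstated by more.

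**The case against.** The strongest objection is rarity. The Post-Treatment visit is timed from the last dose, so a site that scheduled it correctly knew that date. The fallback is reached only when both the dosing-log date and the end-of-treatment date are missing. SAP section 6 places the analysis after all Part 1 patients have discontinued and the database is locked, and SAP 5.2.1 summarises treatment disposition. A patient lost without attending the visit does not produce this error. All of this stands. It limits the reach of the point, but the rule still returns an off-drug date when it is used.

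A second objection is that the dosing sentence is only loose wording. The synopsis, under Treatment Duration, ends dosing at progression, unacceptable toxicity, withdrawal of consent or investigator decision. Nobody could dose up to a visit set 30 days after the last dose. This also stands: the sentences need reconciling, but they do not show that dosing is meant to run to that visit.

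A reader might infer three wider consequences that the documents do not support.
- **Laboratory, ECG and vital-sign values from the Post-Treatment visit become on-treatment because of the fallback.** SAP 5.1.1 already counts everything after the start of study drug as on treatment when the last-dose date is missing. The two rules may serve different purposes, exposure and safety windowing. What remains is that SAP 5.1.1 does not say whether an imputed date still counts as missing.
- **Treatment-emergent adverse events are materially affected.** SAP 4.2.1 also cuts that window at the start of survival follow-up, and protocol 10.6.1.6 ends routine reporting 30 days after the last dose.
- **Protocol 8.5 conflicts with 12.3 over other anticancer therapy.** Section 8.5 says that "nonprotocol anticancer therapies prior to disease progression is not permitted during the treatment phase of this study". Section 12.3 flags events after further therapy following discontinuation, and does not say progression was absent. A patient who stopped for progression satisfies both.

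**Conclusion.** The point holds as a narrow defect in SAP 4.2.7. Read literally, the fallback gives an off-drug last-dose date to any patient who lacks both recorded dates and attended the Post-Treatment visit. For a visit held within its window, G1T38 duration and exposure are overstated by 30 to 40 days (0.99 to 1.31 months), and by more if a later contact date is chosen. Compliance rises only where dosing was interrupted; the compliance figures shown rest on an assumed 21-day interruption.

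The number affected is not given and should be very small. One such patient is visible in the mean of a three-patient dose level and negligible across 36. The consequence is confined mainly to descriptive exposure and compliance summaries. The DLT window is fixed by calendar (SAP 4.2.2) and is not touched.

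It might seem to follow that the Treatment Phase should be redefined to end at the last dose. The documents do not support that. The phase is used as a study epoch that includes the Post-Treatment visit, as in protocol Table 9-1, and the restrictions on other therapy in protocol 8.5 are tied to it. Redefining the phase would change how long they apply.

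**What to change.** **SAP 4.2.7**
- Exclude the Post-Treatment visit, and any contact after it, from the second-step fallback.
- Where a Post-Treatment visit took place, cap the imputed last dose at that visit's date minus 30 days.
- Otherwise, use the last on-treatment visit or contact at which study drug was documented.
- Flag every imputed last-dose date in the exposure listing.

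**SAP 5.1.1.** State whether the date imputed under 4.2.7 also sets the treatment-period window, or whether the inclusive rule applies whenever the recorded date is missing.

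**Phase wording.** Reconcile the sentences on dosing through the end of the Treatment Phase (synopsis, protocol 6.1.1, SAP 2.2) with the phase definition, leaving the definition as it is.

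**Cost.** A few sentences and one listing flag, with no new data. Exposure becomes shorter for affected patients, and some error remains. A date set at the cap can still be up to 10 days late (10/30.4375 = 0.33 months), because the visit may fall at + 40. A date taken from an earlier visit can be too early by up to about one visit interval. With visits every 28 days from Cycle 5, that is about 27 days, or 0.89 months.
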